#### 6.5. WINDOWING CONVENTIONS

No visit windowing will be performed for this study. Summaries and statistical analyses will be based on scheduled (i.e., nominal visit) data. Listings will include scheduled, unscheduled, retest and early termination data. Listings of CS doses will include all add entry fields for Prescribed CS dose for a given visit (both scheduled and unscheduled).

#### 6.6. STATISTICAL TESTS

Unless otherwise noted, all statistical inference will be tested as 2-sided with  $\alpha=0.05$ .

Document:	CCI	Version Number:	Final 2.0
Author:	PPD	Version Date:	12Apr2019
Template No:	CCI	Reference:	CCI
Effective Date:	01Apr2016		

Copyright © 2009, 2010, 2012, 2016 CCI. All rights reserved.  
The contents of this document are confidential and proprietary to CCI. Unauthorized use, disclosure or reproduction is strictly prohibited.

## 6.7. COMMON CALCULATIONS

For quantitative measurements, CFB will be calculated as:

- Test Value at Visit X – Baseline Value

## 6.8. SOFTWARE VERSION

All analyses will be conducted using Statistical Analysis Software (SAS) version 9.4 or higher. The actual SAS version used to perform the analyses will be documented in the Clinical Study Report.

## 7. STATISTICAL CONSIDERATIONS

### 7.1. ADJUSTMENTS FOR COVARIATES AND FACTORS TO BE INCLUDED IN ANALYSES

The following covariates and factors are used in the analyses. For details of their inclusion in the models, see the specific analysis section.

- Baseline daily CS dose (prednisone or equivalent) level (15-40 mg, 41-60 mg); as a categorical variable
- Baseline value
- Treatment group (IGIV-C, Placebo)
- Protocol specified visits (Week 0, Week 3, Week 6, Week 9, Week 12, Week 15, Week 18, Week 21, Week 24, Week 27, Week 30, Week 33, Week 36, Week 39, Week 42, Week 45)
- Treatment-by-visit interaction

### 7.2. MULTICENTER STUDIES

This study will be conducted by multiple investigators at multiple centers internationally. Randomization to treatment arms is not stratified by country or center. The number of subjects per center is expected to be small. Data from this study will be summarized for all centers combined. No center effect will be considered in the statistical models.

---

Document:

Author:

CCI

PPD

Version Number:

Version Date:

Final 2.0  
12Apr2019

Template No: CCI

Effective Date: 01Apr2016

Reference: CCI

Copyright © 2009, 2010, 2012, 2016 CCI. All rights reserved.

The contents of this document are confidential and proprietary to CCI. Unauthorized use, disclosure or reproduction is strictly prohibited.

### 7.3. MISSING DATA

Imputation for missing values will be applied to continuous efficacy endpoints using the LOCF or the WOCF method.

Primary efficacy endpoint of CS dose:

For the primary efficacy endpoint of CS dose, the WOCF method will be applied to subjects who discontinued early from the study with adverse outcomes related to MG, defined as those subjects who met ALL criteria below:

- The primary reason for discontinuation is one of the following: “Adverse Event”, “Death”, “Discontinuation due to MG crisis requiring hospitalization”, or “MG worsening (CS-unresponsive or 2nd episode)”
- The subject had at least one adverse event (AE) with preferred term (PT) of either “Myasthenia gravis crisis” or “Myasthenia gravis”
- The AE is serious, with the reason for seriousness being “Required/Prolonged Hospitalization” or “Resulted in Death”
- The onset date/time of the AE is on or after the start date/time of the first infusion of study medication, i.e., the AE is treatment-emergent

For these subjects, the worst values, i.e., the highest average daily CS dose available among all eligible visits [including the Baseline visit, all post-baseline scheduled visits, and the Early Termination visit(s)], will be carried forward to impute the missing CS dose for all remaining visits.

For subjects who discontinued the study early due to any other reasons, the LOCF method will be used to impute the missing values, i.e., the last non-missing post-baseline CS dose value available among all eligible visits [including all post-baseline scheduled visits and the Early Termination visit(s)] will be carried forward to impute missing values for all remaining visits.

Note for the primary efficacy endpoint of CS dose, the values to be considered as candidates for carrying forward are the derived average daily CS dose at the relevant scheduled visits, incorporating potential changes in the prescribed CS dose within the prior 3 weeks (see section 16.1.1 for derivation details).

Other continuous efficacy variables:

For all other continuous efficacy variables and for all subjects who discontinued the study early, regardless of the reason, the LOCF method will be used to impute the missing values, i.e., the last non-missing post-baseline value (including scheduled, unscheduled, and early termination) will be carried forward to impute missing values for all remaining visits.

All continuous efficacy variables:

In addition, for all efficacy variables, any intermittent missing values up to the last visit will be imputed by

Document: CCI

Author: PPD

Version Number:

Final 2.0

Version Date:

12Apr2019

Template No: CCI

Reference: CCI

Effective Date: 01Apr2016

Copyright © 2009, 2010, 2012, 2016 CCI. All rights reserved.

The contents of this document are confidential and proprietary to CCI. Unauthorized use, disclosure or reproduction is strictly prohibited.

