4.4.7.3 MG Events That Are Not Considered AEs

Given that variations in symptoms are an inherent part of the natural history of MG, all recorded information regarding severity of MG manifestations will be considered efficacy data.

For the purpose of this study, variation in MG symptoms will not be considered an AE unless an exacerbation of MG, or MC requires hospitalization. If a subject is hospitalized for MG, it will be reported as an SAE.

4.4.8 Procedures for Eliciting Reports of and for Recording and Reporting Adverse Events and Suspected Adverse Drug Reactions

The occurrence and follow-up details of all AEs experienced by any of the subjects during the clinical trial, from signature of the *Clinical Trial Written Informed Consent Form* to the last follow-up visit, will be recorded on the AE eCRF entry and in the subject's medical record. If no AE has occurred during the study period, this should also be indicated in the eCRF.

At each visit, AEs will be elicited by asking the individual a non-leading question such as "Do you feel different in any way since the last visit?" Moreover, AEs will also be collected through directly observed events or spontaneously volunteered by the subject. Clearly related signs, symptoms and abnormal diagnostic procedures should preferably be grouped together and recorded as a single diagnosis or syndrome wherever possible. It is responsibility of the investigator to ensure that AEs are appropriately recorded.

The following variables must be recorded on the AE eCRF entry:

- 1. the verbatim term (a diagnosis is preferred)
- 2. date/time of onset
- 3. date/time of resolution
- 4. severity (mild, moderate, severe)
- 5. causality (unrelated, doubtful/unlikely, possible, probable, definite)*
- 6. seriousness (yes, no)
- 7. action taken (with regard to IP)
- 8. other action (to treat the event)
- 9. outcome and sequel (follow-up on AE) *AEs occurring before subject's exposure to IP will be always labeled as "unrelated."

For AEs that occur during infusions, the infusion rate in effect at the time of onset of the AE, the time of onset of the AE and the time of AE change materially in intensity and/or resolves will be captured the eCRF entry.

In addition to the investigator's own description of the AEs, each AE will be encoded by the Sponsor or CRO according to the Medical Dictionary for Regulatory Activities (MedDRA®).

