5.1.3 Efficacy Analyses

5.1.3.1 Primary Efficacy Analyses

The primary endpoint is the percent of subjects achieving a 50% or greater reduction in CS dose (prednisone or equivalent) at Week 39 (Visit 14) from Baseline/Week 0 (Visit 1). The treatment comparison will be analyzed using Cochran-Mantel-Haenszel (CMH) test adjusted for baseline CS dose (15-40 mg versus 41-60 mg). The null hypothesis (H_0) and the alternative hypothesis (H_a) are:

$$H_0: P_1 = P_2$$

 $H_a: P_1 \neq P_2$

Where P1 and P2 represent the percent of subjects achieving a 50% or greater reduction in CS dose in IGIV-C and Placebo group, respectively.

Subjects who discontinued the study early due to the MG worsening will be considered as not achieving a 50% or greater reduction. In subjects who discontinue the study early due to other reasons, the last observation carried forward (LOCF) method will be used to compute the missing CS dose and drive the primary efficacy endpoint. Also, as a sensitivity analysis, the primary efficacy endpoint will be analyzed for all subjects who complete the CS dose up to Week 39 (Visit 14).

Primary Efficacy analyses will be based on the ITT population. For sensitivity analysis, the same analysis will be repeated using the per-protocol population.

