**16.1.2. MISSING DATA METHODS FOR PRIMARY EFFICACY VARIABLE**

Subjects who discontinued the study early with adverse outcomes related to MG will be considered as not achieving a 50% or greater reduction. The missing dose reduction at Week 39 will be imputed using the WOCF method.

For subjects who do not have CS dose prescribed at Week 39 due to other reasons, the LOCF will be used to impute the prescribed CS dose at Week 39. The last non-missing post-baseline value (including scheduled, unscheduled, and early termination) prior to Week 39 will be carried forward to determine whether a subject achieves a 50% or greater reduction at Week 39. Subjects with no post-baseline CS dose will be excluded from analysis.

Refer to section 16.1.4 for analyses on sensitivity to missing data.

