### 16.2.2. MISSING DATA METHODS FOR SECONDARY EFFICACY VARIABLE(S)

#### 16.2.2.1. Missing Data Method for Percent Reduction in Daily CS Dose at Week 39

For subjects who discontinued the study early with adverse outcomes related to MG, the missing percent reduction in CS dose at Week 39 will be imputed using the WOCF method. For subjects who have missing CS dose reduction at Week 39 due to other reasons, the missing CS dose will be imputed using the LOCF approach for continuous endpoints as detailed in Section 7.3.

Missing data will also be handled with the OC approach, where the analysis will be based on observed non-missing data only and subjects with missing data at Week 39 will be excluded from the analysis.

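### The SAP lets a withdrawal for MG worsening count as a responder unless there was also a serious MG adverse event; the protocol scores all such withdrawals as failures, and the change is not declared

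*SAP*

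**What the plan says.** Protocol 5.1.3.1 sets two rules for the primary endpoint. For withdrawals caused by the disease: "Subjects who discontinued the study early due to the MG worsening will be considered as not achieving a 50% or greater reduction". For the rest: "In subjects who discontinue the study early due to other reasons, the last observation carried forward (LOCF) method will be used". The first rule has no adverse-event condition.

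SAP 7.3 replaces the first rule with WOCF, which is "applied to subjects who discontinued early from the study with adverse outcomes related to MG, defined as those subjects who met ALL criteria below". There are four criteria:

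- The primary discontinuation reason is on a list of four: adverse event, death, MG crisis requiring hospitalisation, or MG worsening (unresponsive to CS, or a second episode).
- There is an adverse event with an MG or MG-crisis preferred term.
- "The AE is serious, with the reason for seriousness being" hospitalisation or death.
- The event is treatment-emergent.

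Everyone else falls under the next rule: "For subjects who discontinued the study early due to any other reasons, the LOCF method will be used to impute the missing values".

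SAP 16.1.2 applies the defined term to the primary endpoint: "Subjects who discontinued the study early with adverse outcomes related to MG will be considered as not achieving a 50% or greater reduction". Section 16.2.2.1 does the same for percent reduction ("For subjects who discontinued the study early with adverse outcomes related to MG, the missing percent reduction in CS dose at Week 39" is imputed by WOCF), and 16.3.2.1 for the 75%, CS-free and 7.5 mg endpoints.

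Protocol 4.4.7.3 fixes what can be an MG adverse event: "variation in MG symptoms will not be considered an AE unless an exacerbation of MG, or MC requires hospitalization".

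SAP 3.3, which lists changes from the protocol, names only the move from ITT to mITT.

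**The concern.** MG worsening is on the SAP's own list of WOCF reasons, but the reason alone does not trigger WOCF. Protocol 3.3.3 and 3.10 require withdrawal when an episode does not respond to the CS increase within six weeks, or when a second increase is needed. Neither depends on hospitalisation. A subject withdrawn on those grounds and never hospitalised for MG should have no MG adverse event under 4.4.7.3, so the second and third SAP criteria cannot be met and LOCF applies.

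The endpoint asks whether the steroid dose can be halved while the disease stays controlled. Under LOCF, a taper that failed because the disease worsened can be counted as a success. The wording of SAP 16.1.2 is close to the protocol's, with a narrower defined term in place of MG worsening, so the change is easy to miss.

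The planned sensitivity analyses in SAP 16.1.4 do not help. The per-protocol analysis repeats the same imputation, and the observed-case analysis drops subjects with no Week 39 dose.

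**Working it through.** **The rules side by side, for a subject withdrawn for MG worsening before Week 39**

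| Serious MG adverse event? | Protocol 5.1.3.1 | SAP 7.3 |
|---|---|---|
| Yes, hospitalised or fatal | Non-responder | WOCF, non-responder |
| No | Non-responder | LOCF, either result possible |

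Baseline is eligible for WOCF, so the carried dose is at least the baseline dose and the reduction at most 0%.

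**Can LOCF give a responder?** Inputs: taper steps (Protocol Table 3-1), increase on worsening (Table 3-3: +15 mg below 15 mg/day, +20 mg otherwise), re-taper floor (3.3.4), and the average daily dose between visits (SAP 16.1.1).

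*Example 1, CS-unresponsive, baseline 40 mg.*
- Prescribed 35, 30, 25, 20, 15, 10, 5 mg at Weeks 9 to 27.
- Worsening at Week 30 on 5 mg: 5 + 15 = 20 mg.
- Not improved, withdrawn at Week 36. The Week 33 and Week 36 averages are both 20 mg.
- Reduction = 1 − 20/40 = 50%: a responder. WOCF carries 40 mg, a reduction of 0%.

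*Example 2, second episode, baseline 15 mg.*
- 10 mg at Week 9, 5 mg from Week 12; the optional step to 0 mg is not taken.
- Worsening at Week 18: 5 + 15 = 20 mg. Stable for two visits.
- Re-taper to 15, 10, 5 mg at Weeks 24, 27, 30. Second worsening at Week 33, with a Week 33 average of 5 mg.
- Reduction = 1 − 5/15 = 67%: a responder, who also passes the 7.5 mg endpoint. WOCF carries 20 mg, 33% above baseline.

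Both hold unless a higher dose is recorded at an Early Termination visit or a later unscheduled visit.

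**How many subjects?** The plan's sample size reproduces. With pooled variance, n = [1.96√(2 × 0.5 × 0.5) + 0.842√(0.7 × 0.3 + 0.3 × 0.7)]² / 0.4² = 23.3, so 24 per arm, and 48/0.8 = 60 randomised. The documents give no rate for MG-worsening withdrawals. Assume the 20% discontinuation is spread evenly: 0.20 × 30 = 6 per arm. As an upper case, assume all 6 are MG-worsening withdrawals without a serious MG event, and that a fraction f of them end at or below half of baseline:

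| f (assumed) | 0% | 5% | 10% | 17% |
|---|---|---|---|---|
| False responders per arm, 6f | 0 | 0.3 | 0.6 | 1.0 |

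**What does one subject do near the boundary?** With 30 per arm and m responders in total, the single-stratum CMH statistic is (a − m/2)² / [30 × 30 × m(60 − m) / (60² × 59)], where a is the IGIV-C count. At 18 vs 10, m = 28 and the variance is 3.797, so 4²/3.797 = 4.21 and p = 0.040.

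| IGIV-C vs placebo responders | CMH p | Fisher p |
|---|---|---|
| 18 vs 9 | 0.021 | 0.037 |
| 18 vs 10 | 0.040 | 0.069 |
| 18 vs 11 | 0.073 | 0.12 |
| 17 vs 10 | 0.072 | 0.12 |

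I also split the arms by baseline-dose stratum, with 3, 6, 10 or 12 subjects per arm in the 41–60 mg stratum and responders within one of proportional. CMH p is then 0.037–0.042 at 18 vs 10 and 0.073–0.076 at 18 vs 11.

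**Secondary endpoint.** Using LOCF in place of WOCF for one subject moves a 30-subject arm mean by 50/30 = 1.7 points (Example 1) or (67 + 33)/30 = 3.3 points (Example 2).

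**The case against.** **Safeguards exist.** LOCF accepts Early Termination doses, and SAP 16.1.1 also lets a later unscheduled record enter, expressly to catch dose increases. In a second-episode withdrawal the subject needs a second increase, so a recorded higher dose may remove the false response. This stands as a limit on frequency. It does not restore the protocol rule: the discontinuation visit is requested only if the subject is willing (Protocol 3.11), and in Example 1 the increase is already in the carried dose.

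**The CS-unresponsive route is narrow.** For baselines of 15 to 60 mg in 5 mg steps, without the optional step to 0 mg, it gives a responder only at 40–55 mg and only for worsening at Week 30. Taking that step adds 30 mg (Weeks 27 and 30) and 35 mg (Week 30). This is correct. With the second-episode route added, every baseline has at least one path, taking the re-taper floor as the dose held at the visit before worsening.

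**CMH may not be the operative test.** SAP 16.1.3 moves to exact methods when any cell is below 5, which happens in 23 of the 24 stratified tables examined at 18 vs 10; the stratified exact p there is 0.065–0.072. This is fair. The one-subject flip then lies between 18 vs 9 and 18 vs 10. At the design rates (21 vs 9), Fisher p is still 0.037 with three false placebo responders.

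**Scope.** The protocol rule covers the primary endpoint only, so for the other endpoints the case is consistency, not contradiction. The SAP is also wider in one respect: it adds adverse-event and death withdrawals with a serious MG event.

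**Nothing was hidden.** Protocol 5.1 leaves data handling to the SAP, and the SAP history mentions sponsor feedback on WOCF. Neither identifies a departure from a responder rule that the protocol states outright.

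**Conclusion.** The point holds. For the primary endpoint SAP 7.3 and 16.1.2 contradict Protocol 5.1.3.1, the affected subjects can be scored as responders, SAP 3.3 does not declare the change, and no planned analysis applies the protocol's rule.

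The expected size is small: probably below one false responder per arm. That rests on an even 20% discontinuation and on assumed fractions that the documents do not supply. Because the rule applies to both arms, the direction of bias is not fixed: a false placebo responder can hide an effect, and a false IGIV-C responder can create one. I claim no loss of power. It matters because it reverses a stated rule for the primary endpoint in a trial where one subject can decide a borderline result. It should be fixed.

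**What to change.** In SAP 7.3, for discontinuation before Week 39, make two primary reasons sufficient for WOCF on their own, whatever the adverse-event coding or seriousness: MG worsening (CS-unresponsive or second episode) and MG crisis requiring hospitalisation. Keep the adverse-event test only for the reasons adverse event and death. Use the same trigger in 16.1.2, 16.2.2.1 and 16.3.2.1 so that all CS-dose endpoints agree.

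Alternatively, state and justify the narrower rule in SAP 3.3 and add the protocol rule as a sensitivity analysis of the primary endpoint.

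Protocol 4.4.6.1 exempts hospitalisation that is part of usual MG treatment from seriousness, while 4.4.7.3 makes MG hospitalisation an SAE. Reconcile the two, since any remaining seriousness test depends on them.

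The cost is SAP wording and one derivation flag before database lock. The eCRF reason codes already exist, and neither new data nor a change in sample size is needed. Observed response rates may be slightly lower in either arm.

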4.4.7 Adverse Events of Special Interest

4.4.7.1 Thromboembolic Events

Subjects will be monitored for signs and symptoms of arterial and venous thromboses. In addition, the Grifols Medical Monitor will routinely review reported AEs for possible thromboses. Arterial and venous thromboses will be identified according to definitions in the International Classification of Diseases, Ninth Revision, Clinical Modification (ICD-9-CM). Such thrombotic events include, but are not limited to, DVT, PE, myocardial infarction, cerebrovascular accident, acute coronary syndrome, limb thrombosis, sagittal sinus thrombosis, and portal vein or mesenteric artery thrombosis. All thrombosis will be recorded as AEs, reported accordingly, and if serious, may require early discontinuation from study. See Appendix 7 for details.

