**Analysis Plan**

the closest previous non-missing value. Note that if a subject has missing values immediately after baseline, the baseline observation will not be carried forward and these values will be left as missing, with the exception of the primary efficacy variable of CS dose, for which the baseline value is eligible for the WOCF algorithm only.

For the same efficacy endpoints above that utilize the LOCF/WOCF algorithm, separate analyses will also be performed using observed data only without imputing any missing data. This non-imputation method will be referred to as the OC.

Missing values for the binary endpoints (e.g., whether or not the subject experienced CS dose reduction) will be handled similarly as for the continuous endpoints. First, the LOCF/WOCF algorithm above will be used to impute the (continuous) missing values. The imputed values will then be used to derive the binary endpoints. The binary endpoints will also be analyzed with the OC approach.

Efficacy analyses will be performed on the mITT population using both the LOCF/WOCF and OC approaches with regards to the missing data, which should allow for more robust assessments of efficacy. See Section 16 for the set of analyses using each of the two approaches. The LOCF/WOCF endpoint row in by-visit listings will indicate the value that was used in the LOCF/WOCF efficacy analysis.

The total scores of QMG, MG Composite, MG-QOL 15, MG-ADL and World Health Organization – Five Well Being Index (WHO-5; see Section 16.3.1.14) are calculated and reported in the eCRF. If one or more items are missing at a given assessment, the total score will be set to missing.

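### A subject who dies of a non-MG cause, or stops for a non-MG adverse event, can be carried forward as a Week 39 responder, and no planned sensitivity analysis scores such subjects as failures

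*SAP*

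**What the plan says.** SAP 7.3 gives WOCF to early discontinuers with adverse outcomes related to MG, "defined as those subjects who met ALL criteria below". There are four criteria:

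- the primary reason for stopping is on a short list, which includes adverse event and death;
- "The subject had at least one adverse event (AE) with preferred term (PT) of either" myasthenia gravis crisis or myasthenia gravis;
- that event is serious because of hospitalization or death;
- that event is treatment-emergent.

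Everyone else who stops early falls under the next rule: "For subjects who discontinued the study early due to any other reasons, the LOCF method will be used to impute the missing values". For the responder variables, SAP 7.3 adds: "The imputed values will then be used to derive the binary endpoints". SAP 16.1.2 applies this to the primary variable: "The last non-missing post-baseline value (including scheduled, unscheduled, and early termination) prior to Week 39 will be carried forward to determine whether" the 50% reduction is met. SAP 16.2.2.1 and 16.3.2.1 use the same scheme for percent reduction and for the 75%, CS-free and 7.5 mg variables.

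Protocol 5.1.3.1 has a matching rule outside MG worsening: "In subjects who discontinue the study early due to other reasons, the last observation carried forward (LOCF) method will be used".

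Withdrawal for an adverse event is foreseen. Protocol 3.10 requires it when the event calls for ending treatment. Protocol 4.4.7.1 says of thromboses that they must be recorded and, "if serious, may require early discontinuation from study". Protocol 4.4.7.2 has a similar provision for serious hemolytic anemia.

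SAP 16.1.4 plans two sensitivity analyses of the primary variable: the per-protocol population, and observed cases in the mITT population, where subjects without a Week 39 dose are left out.

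**The concern.** Death appears among the qualifying reasons for WOCF, so a quick reading suggests that deaths are treated as failures. They are not unless the subject also had a serious MG-coded event. A fatal pulmonary embolism in a subject with no such event meets one criterion out of four and goes to last observation carried forward (LOCF). If that subject had already tapered to half of baseline, the analysis records a Week 39 success for someone who has no Week 39 dose.

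A withdrawal for thrombosis or hemolysis takes the same route. Here the subject is alive and does have a steroid dose, so the objection is weaker. Still, the primary objective is steroid reduction at Week 39 with IGIV-C given through Week 36, and someone who stopped for intolerance months earlier has not shown that.

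No section of either document overrides this, and no planned sensitivity analysis shows the result with such subjects counted as failures.

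**Working it through.** **1. The plan's own figures.** Inputs from Protocol 5.2: 70% versus 30%, 80% power, alpha 0.05, 20% discontinuation; two-sided from Protocol 5.1. With pooled variance under the null and no continuity correction:

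n = [1.960 × √(2 × 0.5 × 0.5) + 0.842 × √(0.7 × 0.3 + 0.3 × 0.7)]² / 0.4² = (1.386 + 0.545)² / 0.16 = 23.3, so 24 per group (power 81.2%).

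48 / (1 − 0.20) = 60 in total, or 30 per arm. Both figures reproduce and are not in dispute.

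**2. Which rule applies.** Take a subject with no treatment-emergent MG event leading to hospitalization or death.

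| Event before Week 39 | Listed reason | MG-coded event | Rule |
|---|---|---|---|
| Death, non-MG cause | yes | no | LOCF |
| Stop for a non-MG adverse event | yes | no | LOCF |

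Had the subject also had a hospitalized treatment-emergent MG event, all four criteria would be met and WOCF would apply, whatever the cause of stopping. A subject with no post-baseline CS dose is excluded, not imputed.

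**3. When the carried dose becomes a response.** Inputs: baseline 15 to 60 mg/day (Protocol 3.2.1); taper from Week 9 in steps of 10 mg above 40 mg/day and 5 mg at or below it, every 3 weeks (Protocol Table 3-1; Table 3-2 is the same after halving); average dose over the interval since the previous scheduled visit (SAP 16.1.1). Assumptions: no interruption, each step in force from the day after the visit, baselines in multiples of 5 mg. The average at a visit is then the dose set at the visit before.

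| Baseline (mg/day) | Doses set from Week 9 | First visit with at least 50% reduction | Average there | Reduction |
|---|---|---|---|---|
| 15 | 10, 5 | Week 15 | 5 | 66.7% |
| 20 | 15, 10 | Week 15 | 10 | 50.0% |
| 25 | 20, 15, 10 | Week 18 | 10 | 60.0% |
| 30 | 25, 20, 15 | Week 18 | 15 | 50.0% |
| 35 | 30, 25, 20, 15 | Week 21 | 15 | 57.1% |
| 40 | 35, 30, 25, 20 | Week 21 | 20 | 50.0% |
| 45 | 35, 30, 25, 20 | Week 21 | 20 | 55.6% |
| 50 | 40, 35, 30, 25 | Week 21 | 25 | 50.0% |
| 55 | 45, 35, 30, 25 | Week 21 | 25 | 54.5% |
| 60 | 50, 40, 35, 30 | Week 21 | 30 | 50.0% |

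The lead over Week 39 is 39 − 15 = 24, 39 − 18 = 21 or 39 − 21 = 18 weeks. A stop before the visit shown carries forward as non-response.

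The 50.0% rows are fragile. With a baseline of 40 mg and the last step one day late, the Week 21 average is (1 × 25 + 20 × 20) / 21 = 20.2 mg, just above half, and the first qualifying visit moves on by three weeks.

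**4. Weight of one subject.** 1/30 = 3.3 percentage points, in whichever arm it falls.

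**5. For scale only.** The documents do not split discontinuations by reason, so the count k is an assumption. It runs from 0 to 6, because 20% of 30 is 6 stops per arm from all causes. Start from the planned rates, 21/30 versus 9/30, and turn k IGIV-C responders into non-responders with no change on placebo (unstratified Fisher exact test):

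| k | 0 | 1 | 2 | 3 | 4 | 5 | 6 |
|---|---|---|---|---|---|---|---|
| p | 0.004 | 0.009 | 0.019 | 0.037 | 0.067 | 0.115 | 0.187 |

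One such case would not overturn a result of the planned size. Four in one arm, with no offset in the other, would. This is not a forecast, and a reclassified placebo responder moves the difference 3.3 points the other way.

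**The case against.** The strongest reply concerns living subjects. Those who stop for toxicity are asked to attend an early discontinuation visit and two follow-up visits, 6 and 9 weeks after their last infusion (Protocol 3.8.2.6 and 3.11), with the prescribed CS dose recorded. SAP 6.4 and 16.1.1 turn these into early-termination visits with their own average dose, SAP 7.3 lets LOCF use them, and SAP 16.1.1 adds a later unscheduled visit. A steroid increase recorded there replaces the tapered dose. This stands, although the early discontinuation visit depends on the subject's willingness. It gives little protection in the case of death, where only an unscheduled record could intervene.

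A reader might infer that the rule favours IGIV-C, because placebo is saline and product toxicity can arise only on active treatment. The documents do not support a net direction. They give no toxicity withdrawal rate by arm or by time. Stops before Weeks 15 to 21 count against the arm in which they occur. Placebo subjects who leave later for non-MG reasons also become responders. Nor can a number of affected subjects be read from the 20% rate, which covers all reasons, MG worsening included.

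It is also said that the rule is prespecified, agrees between protocol and SAP for non-MG reasons, and belongs to a Phase 2 proof-of-concept study (SAP 7.4). That is true: this is a design weakness, not a contradiction. Reasons for discontinuation, deaths, adverse-event withdrawals and the carried values are tabulated or listed (SAP 7.3, 9 and 17.1), so each case could be found. Finding cases in listings does not replace an analysis, and the observed-case analysis removes these subjects without counting them as failures.

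**Conclusion.** The point holds in limited form. Without a serious MG-coded event, a subject who dies of another cause before Week 39 can be scored as achieving the primary endpoint, once the taper has reached half of baseline: from the Week 15, 18 or 21 visit by baseline dose, given an uninterrupted taper with steps taken on time. A subject who stops for a non-MG adverse event can be scored likewise, unless a later recorded visit gives an average dose above half of baseline.

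A reader might conclude that every non-MG death or toxicity stop becomes a response. It does not: earlier stops are non-response, and a taper interrupted by worsening can bring the dose back above half of baseline.

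The size is 3.3 points per subject in an arm of 30. The total effect and its direction are unknown from the documents. What is firm is that death is not reliably a failure, and that no planned sensitivity analysis shows the result with these subjects scored as failures.

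**What to change.** 1. In SAP 7.3 and 16.1.2, score death from any cause before Week 39 as non-response for the 50%, 75%, CS-free and 7.5 mg variables. For percent reduction, use the WOCF value. SAP 16.2.2.1 and 16.3.2.1 need the same wording.
2. In SAP 16.1.4, add a sensitivity analysis of the primary variable that scores discontinuation before Week 39 for any adverse event as non-response, in both arms. LOCF stays in the primary analysis for living subjects, because the endpoint is the steroid dose at Week 39 and later dose records can correct the carried value.

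Taking any adverse event, without regard to causality, avoids relying on the suspected-ADR category, which under Protocol 4.4.3 extends to doubtful or unlikely relationships.

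The cost is a few sentences and one extra table, to be settled before unblinding. No new data are needed: the reason for withdrawal is already recorded. Responder rates may come out slightly lower.
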